- State- Trait Anxiety Inventory (STAI)
- Average weekly frequency of migraine headaches for the last 4 week period
- COMPASS-31 score.

Anthropomorphic assessments (body weight, body height, body mass index [BMI]. Pregnancy test results that need to be recorded from chart review or obtained as part of the screening and EKG to rule out any abnormal baseline electrocardiogram such as second and third degree heart block, atrial fibrillation, atrial flutter, recent history of ventricular tachycardia or ventricular fibrillation, or clinically significant premature ventricular contraction, history of prolonged QT interval or a history of clinically significant arrhythmia.

Data will be captured on REDCAP and stored on the secure Hopkins server for this purpose.

2. Treatment Start Visit

At this visit, the patient will receive the gammaCore (nVNS) device and a video instruction will be use to explain how to properly handle the device. Treatment can only start after eligibility has been fully checked and all data collected at screening have been keyed into the trial database. Women of childbearing potential must have a negative urine pregnancy test.

After eligibility is confirmed with the clinical center staff the treatment can begin. The date of starting treatment is the start (ZERO) time for the timing of follow-up visits.

Frequency and duration of nVNS treatment.

The treatment will be self-administered using nVNS and will be applied for 8 weeks; 4 weeks will be used on one side of the neck and other 4 weeks in the contralateral side. A member of the study will provide the proper training on the correct use of nVNS. The patient will be instructed to use the nVNS in place of the rescue medications. When the nauseas gets bad enough that they feel to use a rescue medication they will first use the device on one side of the neck for two 2minute stimulations and wait fifteen minutes to check if the stimulation works. If this does not help either, they will stimulate with an additional 2 stimulations and wait for another fifteen minutes. If there is no improvement rescue medication will be used. nVNS can be used up to, but no more than, 8 times a day.

3. Follow-up Visits

Patients will return for follow-up visits at 4 and 10 weeks after treatment initiation. The specific

procedures to be completed at each of the follow-up visits are:

- Week 4 visit: The following questionnaires should be completed and collected:

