 - Gastroparesis Cardinal Symptom Index Daily Diary (GCSI-DD)
 - Rescue medication uses daily diary- number of pills and type
 - Migraine and headache daily diary
 - Gastrointestinal Symptom Rating Scale (GSRS)
 - Patient Assessment of Upper Gastrointestinal Symptom Severity Index (PAGI-SYM)
 - Beck Depression Inventory (BDI-II)
 - State- Trait Anxiety Inventory (STAI)
 - Average weekly frequency of migraine for the last 4 week period
 - COMPASS-31 score.
 - Global patient impression (GCPI) questionnaire.

Laboratory test results that need to be collected are EKG and urine pregnancy test. Review study of adverse events will be addressed.

- Week 8 visit: This will be the end of study visit. A medical history, including side effect or symptom profile will be collected. The following questionnaires should be completed and collected:
 - Gastroparesis Cardinal Symptom Index Daily Diary (GCSI-DD)
 - Rescue medication uses daily diary- number of pills and type
 - Migraine and headache daily diary
 - Gastrointestinal Symptom Rating Scale (GSRS)
 - Patient Assessment of Upper Gastrointestinal Symptom Severity Index (PAGI-SYM)
 - Beck Depression Inventory (BDI-II)
 - State- Trait Anxiety Inventory (STAI)
 - COMPASS-31 score.
 - Global patient impression (GCPI) questionnaire.
- Week 10 visit: This will be the end of study visit. A medical history, including side effect or symptom profile will be collected. The following questionnaires should be completed and collected:
 - Gastroparesis Cardinal Symptom Index Daily Diary (GCSI-DD)
 - Rescue medication uses daily diary- number of pills and type
 - Migraine and headache daily diary
 - Gastrointestinal Symptom Rating Scale (GSRS)
 - Patient Assessment of Upper Gastrointestinal Symptom Severity Index (PAGI-SYM)
 - Beck Depression Inventory (BDI-II)
 - State- Trait Anxiety Inventory (STAI)
 - COMPASS-31 score.
 - Global patient impression (GCPI) questionnaire.

	Screening & GammaCore treatment Visits (Weeks)		Follow-up Visits: Weeks from start of treatment		
	Screening (0)	Treatment initiation (2)	4	8	10
Consent	X				
Baseline medical	X				
history					
GCSI-DD	X		X	X	X
Rescue Medication Daily Diary	X		X	X	X
Migraine and Headache Daily Diary	X		X	X	X
Collection of GCSI- DD		X	X	X	X
Collection of Rescue Medication Daily Diary		X	X	X	X
Collection of Migraine and Headache Daily Diary		X	X	X	X
PAGI-SYM questionnaire	X		X	X	X
GSRS questionnaire	X		X	X	X
Beck Depression Inventory-II	X		X X	X X	X X

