- Total of 45 patients. This is a pilot study to assess the strength of the signal (improvement) with peripheral VNS for nausea. Since there is evidence that the left and right vagus may have different pathways within the CNS, with the left side being dominant in innervation of center involved in food aversion and nausea (Cell 175, 665–678, 2018), we are proposing to study three groups as follows
 - Group 1; Start with left sided stimulation 15 patients
 - Group 2. Start with right sided stimulation 15 patients
 - Group 3. Both sided stimulation 15 patients
- Our assumptions are as follows, in terms of the number of patients improving in each group

Group 1: 4/15 Group 2: 11/15 Group 3: 7/15

If these assumptions are true, the type I error will be < 0.05

8. Risks³²⁻³⁴

The adverse reactions observed in nVNS studies include:

- i. Shortness of breath (dyspnea), hoarseness, or change in voice during treatment.
- ii. Muscle twitching, discomfort, or pain during stimulation.
- iii. Change in taste (dysgeusia).

These first three reactions resolved after treatment was completed.

- iv. Local skin irritation/inflammation.
- v. Any progression of headache symptoms.

Adverse reactions not seen in the studies, but associated with implanted vagal nerve stimulation devices include:

- vi. Tingling, pricking, or a feeling of "pins and needles" on the skin where the device is applied (paresthesia or dysaesthesia) lasting beyond the treatment period.
- vii. Fainting (syncope), light-headedness, and/or dizziness.
- viii. Sweating.
- ix. Fatigue, depressed mood.
- x. Tinnitus.
- xi. Diarrhea.
- xii. Abnormal heart rhythm.

Adverse events will be evaluated in every follow-up visit. A form of Adverse Event will be completed if the candidate complains of any symptoms, sign, abnormal assessment or any combination of these. An adverse event can be expected side effect that is of a serious nature, or an unexpected side effect/event regardless of severity.

This study will monitor and report adverse events to ensure patient safety to IRB and FDA. Signs and symptoms associated with the adverse event will be graded as to severity by the clinical site staff as mild, moderate, or sever using Version 5.0 of the National Cancer Institute's Common Terminology Criteria for Adverse Events (CTCAE).

9. Benefits

Description of the probable benefits for the participant and for society.

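### The only side rule in section 4 (one side for four weeks, then the other) covers all patients and contradicts Group 3, both-sided stimulation

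*Combined protocol and SAP*

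**What the plan says.** Section 7 (Sample size justification) plans 45 patients in three groups of 15. It motivates them by possible differences between the left and right vagus. The first is "Group 1; Start with left sided stimulation 15 patients", the second is its right-sided counterpart, and the third is "Group 3. Both sided stimulation 15 patients". Each has its own assumed number improving: "Group 1: 4/15 Group 2: 11/15 Group 3: 7/15". The endpoint is a 50% fall in weekly rescue doses from baseline. No treatment weeks are named for it.

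Section 4 (Frequency and duration of nVNS treatment) is the only place that says how the device is applied. Treatment lasts eight weeks, and "4 weeks will be used on one side of the neck and other 4 weeks in the contralateral side". In an exacerbation, "they will first use the device on one side of the neck for two 2minute stimulations and wait fifteen minutes". If that fails, "they will stimulate with an additional 2 stimulations and wait for another fifteen minutes". Rescue medication follows if there is still no improvement, and the device may be used at most eight times daily. No group is mentioned.

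Section 4 (Follow-up Visits) lists what is gathered at each visit. The list headed "Week 4 visit: The following questionnaires should be completed and collected" includes "Rescue medication uses daily diary- number of pills and type".

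**The concern.** Groups 1 and 2 are defined by a starting side, which fits a rule that switches sides after four weeks. Group 3 has no starting side and carries a label that the rule does not allow. Either an exception was intended and never written, or the arm duplicates the other two.

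What is at stake is the three-group comparison. Staff who follow section 4 literally would treat a Group 3 patient exactly like a Group 1 or Group 2 patient. Staff who follow the section 7 label would have to choose the side split themselves, and could choose differently within the same 15 patients. In either case the assumed 7/15 belongs to a regimen that the document does not describe. The missing analysis window adds to this, because the groups differ by side within each four-week period, whereas Groups 1 and 2 do not differ in total side exposure over the full eight weeks.

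**Working it through.** **The plan's own figure.** Section 7 says that the assumed counts give a type I error below 0.05. In total 4 + 11 + 7 = 22 of 45 improve, so 22/45 = 0.489 and the expected number per group is 7.33. Pearson chi-square = [(4 − 7.33)² + (11 − 7.33)² + (7 − 7.33)²] / (15 × 0.489 × 0.511) = 24.67 / 3.75 = 6.58 on 2 df, p = 0.037. The figure reproduces as a p-value for the assumed table. It takes three distinct regimens for granted, so it does not bear on whether they exist.

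**Step 1: apply section 4 as written, then under the reading that the section 7 label suggests.**

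| Group | Weeks 1-4 | Weeks 5-8 | Over 8 weeks |
|---|---|---|---|
| 1 | left | right | 28 days left, 28 right |
| 2 | right | left | 28 days right, 28 left |
| 3, section 4 literally | one side (which is not stated) | the other side | 28 days each, same as Group 1 or 2 |
| 3, two-sided throughout (not written) | both | both | 56 days both |

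The third row is not a distinct arm. The fourth is, but no section states it.

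**Step 2: what is and is not stated for Group 3.**

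| Element | Stated in section 4? |
|---|---|
| Trigger, stimulation length, number per step, 15-minute waits, move to rescue medication | yes, for all patients |
| Limit of eight uses a day | yes, but a use is not defined |
| Side of each stimulation within an episode | no; the first pair is on one side, the second pair has no stated side |
| Whether the week-4 switch applies | no exception given |

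The maximum per exacerbation is 2 + 2 = 4 stimulations, or 4 × 2 = 8 minutes. If a left-plus-right step counts as one use, a two-step exacerbation costs two uses and 8/2 = 4 fit in a day. If it counts as two, the exacerbation costs four uses and 8/4 = 2 fit.

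**Step 3: what an eight-week comparison measures.** Let L, R and B be the mean weekly reduction in rescue doses under left, right and both-sided use, with no order or carry-over effect.

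- Group 1 over eight weeks: (4L + 4R)/8 = (L + R)/2.
- Group 2 over eight weeks: (4R + 4L)/8 = (L + R)/2.
- Group 1 minus Group 2: 0, whatever L and R are.
- Group 3, if two-sided throughout, minus either: B − (L + R)/2, which compares concurrent with sequential use and says nothing about left against right.
- Weeks 1-4 only: the three groups estimate L, R and B separately.

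A responder endpoint built on pooled weekly doses mixes the two sides in the same way.

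**Step 4: size.** Group 3 is 15/45 = 33% of the patients planned in section 7. Weeks 1-4 supply 4 × 7 = 28 of 8 × 7 = 56 treatment diary days.

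**The case against.** The best defence is that the intention is plain: two groups start on a side, one does not, and staff training with an instruction video would supply the detail. The contrast in labels does make an exception likely. But the training has to teach something, and the document gives no side allocation for it to teach.

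Both-sided could instead mean both sides over the eight weeks. Groups 1 and 2 already get that, so the arm and its separate 7/15 would have no basis. Nor can the second pair of stimulations be read as the two-sided element. Its side is not stated, it is not tied to Group 3, and a patient who responds to the first pair would still be treated on one side only.

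Two objections stand in full.

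- Section 4 gives most of the regimen. A reader might infer that Group 3 has no dosing instruction at all. The document does not support that, because only the side allocation, the switch rule and the daily count are missing.
- A reader might infer that only weeks 1-4 separate the groups by side. If Group 3 is two-sided throughout, weeks 5-8 separate them too: right, left and both. The case for weeks 1-4 is that they come before any switch and are free of carry-over. It is a reasoned preference, and the text does not force it.

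It is also fair that this is a pilot. The precision of a 15-patient arm would be the same if its regimen were fully specified, so it does not measure this defect.

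**Conclusion.** The contradiction is real and confined to one arm and the three-group comparison. The side rule covers all patients and, applied as written, leaves Group 3 (15 of 45, 33%) with no regimen distinct from Groups 1 and 2. An analysis pooled over eight weeks could not show an effect of side, and the plan does not rule one out.

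This rests on three assumptions.

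- The group sizes are those in section 7. Section 4 speaks of about 30 patients and no groups, so the one-third share holds only for the section 7 design.
- Groups 1 and 2 switch at week 4, as section 4 says.
- Step 3 leaves out order and carry-over effects. With them, a pooled difference between Groups 1 and 2 could appear, but it would reflect sequence and could not be read as side.

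Two wider conclusions might be drawn and are not supported. The trial as a whole is not compromised, because the principal objective, rescue medication use under treatment, does not depend on how Group 3 divides its stimulation between sides. A safety problem is not shown either: the daily limit is not said to vary by group, and only the way of counting is open.

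It should be fixed before the first Group 3 patient is trained.

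**What to change.** 1. In section 4, limit the one-side and week-4-switch sentences to Groups 1 and 2.
2. Add a Group 3 rule. One example is one left and one right stimulation in each step for all eight weeks: (1 + 1) × 2 steps = 4 per exacerbation, the same maximum as the other groups, with the same waits.
3. State how a left-plus-right step counts toward the eight daily uses.
4. In section 7, make weeks 1-4 the window for the three-group comparison. Keep weeks 5-8 as supportive data and for the within-patient left/right contrast in Groups 1 and 2.

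The cost is a short amendment to the dosing paragraph, the device training and section 7. The rescue medication diary is already collected at week 4, so no visit or questionnaire is added.

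There are two downsides. Under the example split, each side in Group 3 gets at most 2 stimulations per exacerbation against 4 in Groups 1 and 2 (if those groups put both pairs on the same side), so side is partly mixed with dose per side. The main group comparison also uses 28 of 56 diary days.

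If the section 4 rule really was meant for everyone, the consistent alternative is to delete Group 3 and its 7/15 and justify the size again for two starting-side groups. That gives up the both-sided question.

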The vagus nerve plays a key role in regulation of nausea and vomiting, and there is evidence of vagus afferent effects on nociception, which suggests that electrical stimulation modulates nauseas and vomiting. The current proof of concept study explores the possibility that non-invasive vagus nerve stimulation (nVNS) could have clinical effects similar those of an implanted gastric electrical stimulation device in patients with symptoms of gastroparesis. GES report some complications, the main one being the infections of subcutaneous pocket, inflammation over implant site, device migration/erosion, lead penetration, extra-abdominal pain, seroma and hematoma. Less common complications include erosions of the abdominal wall by the device, penetration of the leads through the gastric wall, or tangling of wires in the generator pocket and formation of adhesions. GES is relatively expensive treatment with the high cost of the device and for the surgical procedure. ²⁰⁻²²

gammaCore (nVNS) is the first non-invasive, handheld medical device²³ applied on the side of the neck and sends gentle, patented mild electrical stimulation through the skin to activate the vagus nerve. nVNS offers a potential alternative to GES that could eliminate significant risks of injury or illness or identify likely responders to implantable neurostimulator including implanted VNS (iVNS). nVNS could provide a more effective and safer alternative to the use of traditional rescue medications.

nVNS primarily stimulates myelinated sensory afferent vagus nerve fibers as they ascend through the neck in the carotid sheath. nVNS has been cleared for the acute and preventive treatment of migraine and the acute and preventive treatment of cluster headache by the Food and Drug Administration (FDA) and is also CE marked and used in several all forms of primary headache. ^{24, 25}

The hypothesis of the pilot study is that nVNS will result in relief of nausea by modulation of vagal nerve activity.

- **2. Objectives** (include all primary and secondary objectives)
- The principal objective of this open label pilot study is to evaluate whether acute treatment
 of nausea exacerbations with nVNS will be effective in reducing the use of rescue
 medications.
- Secondary objectives of this study include:
 - o Determine the nature and incidence of adverse effects.

- Exploratory objectives
 - o Determination of the effects of nVNS (or correlation with response) use on:

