1. Screening visit and baseline data collection

Study participants will come from the patient rosters of study physicians. Patients who appear to be eligible after chart review and completion of standard of care test and procedures will be invited to undergo screening for the trial. Patients considered by the clinical center investigator as likely to be eligible for participation in the trial may be consented, registered and screened at a visit that is a part of the ongoing clinical care of the patient.

An open label pilot study to be conducted at Johns Hopkins Bayview Medical Center over 9 months to evaluate with nVNS for the symptomatic exacerbations of nauseas in patients with gastroparesis or CUNV. Approximately 30 patients will be enrolled in the study. Inclusion criteria will include patients 18 years or older with symptomatic nausea, vomiting and other symptoms suggestive of chronic nausea and vomiting of presumed gastric origin (Gastroparesis or CUNV). All the participants will come from the patient roster of the study physicians from the Division of Gastroenterology, Department of medicine: [name] (Principal Investigator), and [name].

In order to minimize the need for research-only in-person visits, telemedicine visits may be substituted for in person clinical trial visits or portions of clinical trial visits where determined to be appropriate and where determined by the investigator not to increase the participants risks. Prior to initiating telemedicine for study visits the study team will explain to the participant, what a telemedicine visit entails and confirm that the study participant is in agreement and able to proceed with this method. Telemedicine acknowledgement will be obtained in accordance with the Guidance for Use of Telemedicine in Research. In the event telemedicine is not deemed feasible, the study visit will proceed as an in-person visit. Telemedicine visits will be conducted using HIPAA compliant method approved by the Health System and within licensing restrictions

Revisions to the informed consent process are being permanently adopted for this research. Teleconsent will be used as opposed to in person consenting where possible to reduce unnecessary in person encounters specifically for a consent procedure. In the event teleconsent is utilized, participants will be provided with a copy of the Informed Consent prior to the teleconsent meeting either via email, fax, mail or previously provided during an in person visit.

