- Currently implanted with an electrical and/or neurostimulator device, including but not limited to cardiac pacemaker or defibrillator, vagal neurostimulator, deep brain stimulator, spinal stimulator, bone growth stimulator, or cochlear implant.
- History of carotid endarterectomy or vascular neck surgery on the right side.
- Implanted with metal cervical spine hardware or has a metallic implant near the gammaCore stimulation site.
- Any other condition, which in the opinion of the investigator would impede compliance or hinder the completion of the study.
- Failure to give informed consent.

6. **Drugs/ Substances/ Devices**

gammaCore Sapphire (nVNS) ²³⁻²⁵

Description:

nVNS is a multi-use, hand-held, rechargeable, portable device consisting of a rechargeable battery, signal-generating and -amplifying electronics, and a control button for the patient to control the signal amplitude. The device provides visible (display) and audible (beep) feedback on the device and stimulation status. A pair of stainless steel surfaces, which are the skin contact surfaces ("stimulation surfaces"), allow the delivery of a proprietary electrical signal. The patient applies electroCore-approved gel to the stimulation surfaces to maintain an uninterrupted conductive path from the stimulation surfaces to the skin on the neck. Tubes of electroCore-approved gel are provided with each unit and refill kit for this purpose. The stimulation surfaces are capped when not in use.

7. Study Statistics

Data analysis will be performed at Mayo Clinic Scottsdale, Arizona by [name], ([contact]). This site will no recruit participants.

Johns Hopkins will serve as coordinating center, responsible for overall data management, monitoring and communication among both sites, and general oversight of the conduct of this protocol.

Outcome measures

Primary: The primary outcome measure is the average daily use of rescue medications for exacerbation of nausea/vomiting.

Sample size justification

- Primary endpoint: Improvement in nausea control, as defined by a 50% reduction n the number of weekly doses of rescue medications, compared with baseline.

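### The sample size rests on a comparison of three active-stimulation groups, which does not address the principal objective; no primary analysis or precision is stated for the change in rescue use

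*Combined protocol and SAP*

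**What the plan says.** Section 2 (Objectives) states one principal objective, which opens: "The principal objective of this open label pilot study is to evaluate whether acute treatment". In short, it asks if using the device during a nausea flare lowers rescue medication use. The secondary objective is adverse effects. The exploratory objectives cover gastrointestinal symptom scales, depression and anxiety, headache, and autonomic symptoms. None mentions left, right or both-sided stimulation.

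Section 7 (Study Statistics) gives the outcome as follows: "The primary outcome measure is the average daily use of rescue medications for exacerbation of nausea/vomiting". For sizing it uses a responder endpoint, a 50% reduction in "the number of weekly doses of rescue medications, compared with baseline". It gives the purpose of the sample thus: "This is a pilot study to assess the strength of the signal (improvement) with peripheral VNS for nausea".

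The justification itself then turns to three groups of 15, all treated with the device: left first ("Start with left sided stimulation 15 patients"), right first, and both sides. Under "Our assumptions are as follows, in terms of the number of patients improving in each group" it lists 4/15, 11/15 and 7/15, and concludes that the type I error will be below 0.05 if these hold. It names no test, power, reference responder rate or precision for the overall change. Section 4 (Screening visit and baseline data collection) gives a different total: "Approximately 30 patients will be enrolled in the study".

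**The concern.** The principal objective is about change from baseline in everyone treated. The one inferential statement in the plan is about something else, namely whether three treated groups differ from each other. A device that worked equally well on every side would give no group difference. A group difference, if found, would not by itself show that rescue use fell.

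Two things are at stake. The planned number of patients has no stated link to the main question. And because no primary analysis of the change is specified, the choice of summary (daily use or responder share, which weeks, pooled or by group) is left open until open-label data have been seen.

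**Working it through.** **Inputs.** From section 7: 15 per group; responders 4, 11 and 7, total 22/45 = 48.9%; threshold 0.05. From section 4: about 30 patients, taken here as 10 per group (an assumption, since section 4 describes no groups). The test is inferred, because none is named.

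**1. Reproducing the plan's figure.** Under equal rates each group expects 15 × 22/45 = 7.333 responders. The Pearson statistic is Σ(xᵢ − 7.333)² / [15 × p(1 − p)] with p = 0.4889.
- Numerator: (−3.333)² + (3.667)² + (−0.333)² = 11.111 + 13.444 + 0.111 = 24.667.
- Denominator: 15 × 0.4889 × 0.5111 = 3.748.
- Statistic: 24.667 / 3.748 = 6.58 on 2 df, so p = exp(−6.58/2) = 0.037.

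The likelihood ratio test gives 0.033 and the Fisher-Freeman-Halton exact test 0.046. All are below 0.05, so the plan's figure reproduces as a p-value for a difference among the groups. It cannot be a one-sample test of benefit as written, because no reference rate is given.

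**2. What that test does when every side works equally.** I summed the product of three Binomial(15, p) probabilities over all outcomes with a Pearson statistic above 5.99.

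| Common responder rate | Three-group test rejects |
|---|---|
| 10% | 3.5% |
| 4/15 (26.7%) | 5.1% |
| 22/45 (48.9%) | 5.0% |
| 11/15 (73.3%) | 5.1% |
| 90% | 3.5% |

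The rejection rate is identical at 10% and at 90%. The test carries no information on the level of response.

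**3. Its power on its own terms.** With true rates 4/15, 11/15 and 7/15, the same enumeration gives 66% at 15 per group and 43% at 10 per group.

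**4. What the same patients can say about the principal objective.** Exact (Clopper-Pearson) 95% limits are the 0.025 quantile of Beta(x, n − x + 1) and the 0.975 quantile of Beta(x + 1, n − x).
- 22/45 (48.9%): 33.7% to 64.2%, about ±15 points.
- 15/30 (50.0%): 31.3% to 68.7%, about ±19 points.
- 33/45 (11/15 in every group, 73.3%): 58.1% to 85.4%.

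**5. Why a reference rate is needed.** The documents give none, so I assumed a range. With 45 patients, one-sided alpha at most 0.025 and a true rate of 22/45:

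| Assumed reference rate | Responders needed | Power |
|---|---|---|
| 10% | 10 | over 99.9% |
| 20% | 15 | 98.8% |
| 30% | 21 | 67.2% |
| 40% | 26 | 14.8% |

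The same 22/45 can be decisive or uninformative, depending on a number that the plan does not state.

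**The case against.** The strongest reply is that the sample can answer the principal objective. The responder endpoint is defined against each patient's own baseline, and section 7 gives the purpose as gauging improvement. Equal benefit of 11/15 in each group would be visible as 33/45, with limits of 58% to 85%. This stands. A reader might infer that the study cannot address its objective, or that equal benefit on all sides would be reported as no signal. The documents do not support either reading: the before-after data will exist, and nothing says that a null group difference will be taken as failure of the device. What is missing is a plan that uses those data as its primary analysis and rests its size on them.

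It is also fair to say that the three-group test is an inference. The inference is reasonable, since the figure reproduces under three versions of the test, but it should be labelled as one.

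A reader might further infer that a significant group test could easily arise from one side being inert and another harmful. That is weak, because harm can only lower an already low responder share. At assumed rates of 20%, 2% and 20% the test rejects about 19% of the time, and at 10%, 2% and 10% about 7%.

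That this is a pilot does not remove the point. A pilot may well be sized on precision, but this plan states no precision for its main question and makes an error claim about a different one.

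**Conclusion.** The point holds as a mismatch between objective and justification. The only stated basis for 45 patients is a between-group contrast that no objective asks for and that rejects about 5% of the time or less under any common response rate. The principal objective has no named primary analysis and no stated precision.

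The Pearson p-value and the rejection rates need only the plan's group size and responder counts, given the inferred test. The 43% figure also assumes that 30 patients would be split equally. The power figures against a reference rate rest on assumed rates outside the documents; any power figure for a pooled change in daily use would likewise rest on assumed rates and variability, and must be labelled so.

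A pooled fall in rescue use would be a change, not proof of a device effect. Without a control it cannot be separated from regression to the mean, placebo response, or the instruction in section 4 to use the device before rescue medication.

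**What to change.** In section 7:
- Make the primary analysis the pooled within-patient change from baseline in all treated patients, using the plan's own outcomes with 95% confidence intervals: average daily rescue use, and the share of patients with a 50% reduction in weekly doses. Say which of the two is primary and which treatment weeks count.
- Replace the type I error sentence with a justification by precision, at whichever total is settled on: 34% to 64% at 22/45, or 31% to 69% at 15/30. Reconcile the 45 with the figure of about 30 in section 4.
- State in advance, with its source, the reference responder rate against which the share will be read.
- State that, without a control, the pooled change does not isolate the effect of the device.

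In section 2, add left, right and both-sided stimulation as a named secondary or exploratory comparison. In section 7, say that a null group difference is not evidence of no effect.

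The cost is rewording of sections 2 and 7 and reconciling the total in section 4. No new patients or data are needed. The downside is that the side comparison loses its headline position.
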